10.1.9. Publication Policy

- The results of this study may be published or presented at scientific meetings. If this is foreseen, the Investigator agrees to submit all manuscripts or abstracts to the Sponsor before submission. This allows the Sponsor to protect proprietary information and to provide comments.
- The Sponsor will comply with the requirements for publication of study results. In accordance with standard editorial and ethical practice, the Sponsor will generally support publication of multicenter studies only in their entirety and not as individual site data. In this case, a coordinating Investigator will be designated by mutual agreement.
- Authorship will be determined by mutual agreement and in line with the International Committee of Medical Journal Editors authorship requirements.

10.2. Appendix 2: Clinical Laboratory Tests

- The clinical laboratory tests detailed in [Table 5](#) will be performed by a central laboratory, except if noted otherwise, at timing/frequency detailed in the SoA (Section [1.3](#)). Laboratory tests will be performed under fasting conditions (≥ 10 hours).
- Protocol-specific requirements for inclusion or exclusion of subjects are detailed in Section [5](#).
- Additional tests may be performed at any time during the study as determined necessary by the Investigator or required by local regulations.
- Investigators must document their review of each laboratory safety report.

Table 5: Protocol-Required Laboratory Assessments

Hematology	
White blood cell count (WBC) with differential (Neutrophils, Lymphocytes, Monocytes, Eosinophils, Basophils – absolute and %)	Red blood cell (RBC) RBC Indices: Mean corpuscular volume (MCV), mean corpuscular hemoglobin (MCH), %Reticulocytes
Hemoglobin	Hematocrit
Platelet count	Red cell Distribution Width
Coagulation factors: prothrombin time (PT), international normalized ratio (INR), activated partial thromboplastin time (aPTT)	
Biochemistry	
Alanine Aminotransferase (ALT)	Aspartate Aminotransferase (AST)
Alkaline phosphatase (ALP)	Gamma-glutamyl transferase (GGT)
Total bilirubin, Indirect/direct bilirubin	Albumin
Calcium	Blood urea nitrogen (BUN)
Sodium	Creatinine
Chloride	Creatine kinase
Magnesium	Bicarbonate
Potassium	Lactate dehydrogenase
Phosphorus/	Total protein
Glucose (fasting)	Total cholesterol
	Uric acid
Serum lipids: triglycerides, high-density lipoprotein cholesterol (HDL-c), low density lipoprotein (LDL-c), non-HDL-c	

Urinalysis (spot urine)	Full urinalysis (dipstick plus microscopic evaluation) to be performed only at the Screening and Week 48/ET visits). A reflex microscopic urinalysis should be performed if the result of the urinalysis is abnormal or at the discretion of the Investigator or delegate.
Other Study-Specific Laboratory Assessments Pegozafebrin (to be evaluated by bioanalytical laboratory) Serum and urine human chorionic gonadotropin (hCG) pregnancy test for women of childbearing potential FSH (for confirmation of menopausal status in women under the age of 45 with >12 months amenorrhea not using hormonal contraception or hormone replacement therapy) Luteinizing hormone (LH), FSH and estradiol (only for WOCBP who are not on hormonal contraception) Thyroid panel: TSH, FT4 and TT3 Night-time salivary cortisol (NSC)* * NSC samples must be collected between 8:00pm and 12:00am before submitting the sample for processing at the specified visit. If sample is not collected during this time, repeat sample must be collected. If screening value is >15 nmol/L, Medical Monitor (or designee) may request further workup should the value be of clinical concern; however, values > 15 nmol/L will not be exclusionary. The screening NSC is a safety assessment, and not an eligibility criteria. The screening assessment should be performed as early as possible during the screening period. Subjects should be provided with NSC collection kit at the first screening visit, when possible, to allow sample collection return at the following clinic visit. For on-treatment values that are >15.0 nmol/L AND above the screening value, a repeat NSC should be performed (sample should be collected at approximately the same time as the screening sample). If this repeat assessment is still > 15.0 nmol/L AND above the screening value, an additional screening test for hypercortisolism will be done (either overnight dexamethasone (1 mg) suppression test or a 24 h collection for urinary free cortisol). Medical Monitor (or designee) will provide guidance on the appropriate assessment based on	Insulin High-sensitivity C-reactive protein (hsCRP) Hemoglobin A1c (HbA1c) Insulin-like growth factor-1 (IGF-1), total Adiponectin, total C-peptide Enhanced liver fibrosis (ELF) panel including concentrations of serum biomarkers: tissue inhibitor of matrix metalloproteinases-1 (TIMP-1), amino-terminal type 3 procollagen peptide (P3NP), and hyaluronic acid (HA) N-terminal type 3 propeptide of collagen (Pro-C3) Fasting free fatty acids (FFA) and Adipo-IR index (fasting FFA x fasting insulin) ^a FIB-4 index (derived calculation) Alpha feto-protein (AFP) (for F4 patients only) MELD Na ⁺ (for F4 patients only)

the individual subject for subsequent test values that are also >15 nmol/L based on the subject profile.

Urine drug screen including amphetamines, barbiturates, cocaine metabolites, opiates, benzodiazepines and cannabinoids will be done at local laboratory using a standardized kit during screening period by Day 1. If cannot be performed during screening, test can be performed on Day 1, but must be completed before randomization procedures start.

Serology: HIV 1 and 2 antibodies, hepatitis B surface antigen (HBsAg), hepatitis C virus antibody, and HCV RNA (only if HCV antibody-positive)

Immunogenicity:

Antibody to pegozafermin and NAb
Endogenous FGF21

Bone markers: carboxy-terminal collagen crosslinks (CTX), N-terminal propeptide of type 1 collagen (P1NP), osteocalcin

Plasma and serum samples for exploratory biomarkers

Biomarkers from RNA/DNA

Pharmacogenomics sample

10.3. Appendix 3: Adverse Events: Definitions and Procedures for Recording, Evaluating, Follow-up, and Reporting

10.3.1. Definition of AE

AE Definition

• An AE is any untoward medical occurrence in a clinical study subject, temporally associated with the use of IP, whether or not considered related to the IP.• NOTE: An AE can, therefore, be any unfavorable and unintended sign (including an abnormal laboratory finding), symptom, or disease (new or exacerbated) temporally associated with the use of IP.

Events Meeting the AE Definition

• Any abnormal laboratory test results (hematology, clinical chemistry, or urinalysis) or other safety assessments (e.g., ECG, radiological scans, vital signs measurements), including those that worsen from baseline, considered clinically significant in the medical and scientific judgment of the Investigator (i.e., not related to progression of underlying disease). A clinically significant abnormality is a confirmed abnormality (by repeat testing) that is changed sufficiently from Baseline so that in the judgment of the Investigator a change in management is warranted. This alteration may include: monitoring the laboratory test further, initiating other diagnostic tests or procedures, changing ongoing treatment, or administering new treatment.• Exacerbation of a chronic or intermittent pre-existing condition including either an increase in frequency and/or intensity of the condition.• New conditions detected or diagnosed after IP administration even though it may have been present before the start of the study.• Signs, symptoms, or the clinical sequelae of a suspected drug-drug interaction.• Signs, symptoms, or the clinical sequelae of a suspected overdose of either IP or a concomitant medication. Overdose per se will not be reported as an AE/SAE unless it is an intentional overdose taken with possible suicidal/self-harming intent. Such overdoses should be reported regardless of sequelae.

Events NOT Meeting the AE Definition

1. Any clinically significant abnormal laboratory findings or other abnormal safety assessments which are associated with the underlying disease, unless judged by the Investigator to be more severe than expected for the subject's condition.2. The disease/disorder being studied or expected progression, signs, or symptoms of the disease/disorder being studied, unless more severe than expected for the subject's condition.3. Medical or surgical procedure (e.g., endoscopy, appendectomy): the condition that leads to the procedure is the AE.4. Situations in which an untoward medical occurrence did not occur (social and/or convenience admission to a hospital).5. Anticipated day-to-day fluctuations of pre-existing disease(s) or condition(s) present or detected at the start of the study that do not worsen.

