8.2.3. Electrocardiograms

- 12-lead ECG will be recorded as single bedside measurements using an ECG machine that automatically calculates the heart rate and measures PR, QRS, and QT (QTcF) intervals.
- Subject to be resting for at least 2 minutes prior to ECG.
- A central reviewer will be used; instructions will be provided in the imaging manual. ECG tracing should be provided to the central reader within 72 hour of assessment.

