8.2.5. Clinical Safety Laboratory Assessments

See Appendix 2 (Section 10.2) for the list of clinical laboratory tests to be performed and the SoA (Section 1.3) for the timing and frequency. Laboratory tests should be performed under

fasting conditions (≥ 10 hours). Fasting includes food and all beverages except for non-mineral water. It is recommended that subjects abstain from consumption of alcoholic beverages for at least 24 hours before laboratory test assessments. It is recommended that subjects refrain from strenuous activities.

The Investigator must review the laboratory report, document this review, and record any clinically relevant changes occurring during the study in the AE section of the eCRF. The laboratory reports must be filed with the source documents. Clinically significant abnormal laboratory findings are those that are not associated with the underlying disease, unless judged by the Investigator to be more severe than expected for the subject's condition.

All laboratory tests with values considered clinically significantly abnormal during participation in the study or within 28 days after the last dose of IP should be repeated until the values return to normal or baseline or are no longer considered clinically significant by the Investigator.

If such values do not return to normal/baseline within a period of time judged reasonable by the Investigator, the etiology should be identified, and the Sponsor notified.

All protocol-required laboratory assessments, as defined in Appendix 2 (Section 10.2), must be conducted in accordance with the relevant study manual and the SoA (Section 1.3).

If laboratory values from non-protocol specified laboratory assessments performed at the institution's local laboratory require a change in subject management or are considered clinically significant by the Investigator (e.g., SAE or AE or skipping of dose), then the results must be recorded in the eCRF and the Sponsor should be notified.

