4.2. Extension Study Endpoints

4.2.1. Primary Endpoints

- Frequency and severity of TEAEs and SAEs at Week 48

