- ICE-1: Discontinuation of treatment due to lack of efficacy.
- ICE-2: Discontinuation of treatment due to adverse events (AE).
- ICE-3: All other events, i.e., protocol deviation, etc.

The primary analysis will use all observed outcomes at Week 24, regardless of actual treatment. All outcomes collected from patients experiencing this ICE after the actual ICE will be used in the analysis and missing values resulting from any ICE will be imputed assuming an imputation model informed by observed outcomes from similar patients with this type of ICE. The imputation model will include terms for the randomized treatment arm and the type of ICE(s) experienced by patients with missing outcomes, i.e., ICE-1,2,3 (as defined above) or None. The final inference following multiple imputation (MI) will be conducted using Rubin's combination rules.

Although the ICEs' defined above will be all handled by the same treatment policy strategy for the primary estimand, various sensitivity analyses (SA) will be conducted that will incorporate different strategies, depending on the type of ICE. For the purposes of sensitivity analysis, patients who experienced any of the listed ICEs (ICE-1,2,3), the outcomes for the primary efficacy endpoint will be considered missing starting from the occurrence of each ICE (even if outcomes are collected following an ICE) and then the missing outcomes will be imputed using appropriate imputation strategies.

For ICE-1, the SA will use the "return to baseline" hypothetical strategy, implying no benefits have been received for such patients from randomization until the end of the treatment period. The missing outcomes will be imputed using a relevant regression model fitted to the baseline data within each treatment arm with patient age, gender, baseline NAS score and stratification factors included as covariates.

For ICE-2, SA will be handled with the "control-based" hypothetical strategy implying that patients would have switched to the control treatment (i.e., placebo) starting from the occurrence of ICE-2 to the end of the treatment period. The missing outcomes will be imputed from a similar regression model fitted to the placebo arm alone with patient age, gender, baseline NAS score and stratification factors as covariates.

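### The AE definition makes repeat-test confirmation part of clinical significance, in conflict with its own general definition and Section 8.2.5, so abnormalities that were acted on may be recorded inconsistently

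*Protocol*

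**What the plan says.** Protocol Section 8.3 sends the reader to Appendix 3 for the definition of an AE. There, the note to the general definition in Section 10.3.1 reads: "An AE can, therefore, be any unfavorable and unintended sign (including an abnormal laboratory finding), symptom, or disease", where the event is linked in time to use of IP. Nothing in it asks for a second test.

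The list of events that meet the definition follows. Its first bullet covers laboratory results "or other safety assessments (e.g., ECG, radiological scans, vital signs measurements), including those that worsen from baseline", provided they are "considered clinically significant in the medical and scientific judgment of the Investigator". The bullet then defines its own term: "A clinically significant abnormality is a confirmed abnormality (by repeat testing) that is changed sufficiently from Baseline", to the point where the investigator thinks a change in management is warranted. The same list also admits conditions newly found after dosing.

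Section 8.2.5 deals with laboratory tests only. It tells the investigator to enter clinically relevant changes in the AE section of the eCRF. It describes clinically significant findings by their relation to the underlying disease, with no mention of a repeat. Values already judged clinically significant "should be repeated until the values return to normal or baseline or are no longer considered clinically significant by the Investigator".

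Section 10.3.4 adds that an event that is not an AE under 10.3.1 cannot be an SAE, even when a seriousness criterion is met. SAP Section 5.5 draws TEAEs from AEs, and SAP Section 4.2.1 makes "Frequency and severity of TEAEs and SAEs at Week 48" the primary endpoint of the Extension Study.

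**The concern.** Read literally, the first bullet of 10.3.1 leaves out an abnormality that prompted treatment but was normal at the next measurement, and one that nobody measured again. Other text in the same protocol lets both in. A site that follows the bullet and a site that follows 8.2.5 or the general definition can record the same finding differently, and both can claim to have followed the protocol.

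What is at stake is ascertainment. TEAE and SAE frequency and severity is the Extension's primary endpoint and a safety endpoint of the Main Study. An event that was never entered as an AE cannot be recovered when the AE tables are made.

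**Working it through.** No arithmetic applies, so the passages are set side by side.

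**1. Order of judgement and repeat.** In 8.2.5 the investigator judges a value significant and repeats it because of that judgement. In 10.3.1 the repeat comes first, since without it the abnormality is not clinically significant. The bullet is also circular: it lists further monitoring of the test among the changes in management that mark a significant finding, yet it needs a repeat before the finding counts.

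**2. One finding, three readings.** Take a laboratory value that led to treatment and was normal at the repeat.

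| Text followed | Recorded as an AE? |
|---|---|
| 10.3.1, first bullet | No, because it was not confirmed |
| 10.3.1, general definition | It can be, as an unfavourable sign |
| 8.2.5 | Yes, as a clinically relevant change |

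**3. Consequence downstream.** If the answer is no, 10.3.4 also rules out an SAE. SAP 5.5 then gives no TEAE, and the AE summaries in SAP 7.10.1, repeated for the final analysis under 7.12.1, do not contain the event.

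**4. Which assessments are exposed.**

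| Assessment | Repeat provided for in the protocol |
|---|---|
| Laboratory | Yes. 8.2.5 requires it for values judged significant, up to 28 days after the last dose. 7.1.1 (transaminases) and 8.2.5.3 (salivary cortisol) have their own repeat rules |
| Blood pressure, pulse | Measured in duplicate from randomization (8.2.2) |
| ECG | "12-lead ECG will be recorded as single bedside measurements" (8.2.3). The Schedule of Activities allows a further ECG if clinically indicated but does not require one |
| DXA | Day 1, Week 24 and Week 48/ET in the Schedule of Activities. A finding at the last scan has no scheduled confirmation |

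Laboratory findings are thus exposed mainly when the repeat is normal. ECG and final-visit DXA findings are exposed because a repeat may never be made.

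**5. Size.** The number of events missed would be: (abnormalities that were acted on) × (share not confirmed by a repeat) × (share of those not recorded by another route). The documents give none of the three factors, so no estimate can be derived from them.

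**The case against.** Several objections have force.

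- **Other routes to an AE exist.** The general definition, the entry for newly found conditions, the recording rule in 8.2.5 and the instruction in 10.3.5 to record the diagnosis all admit events without a repeat. A reader might infer that an abnormality is an AE only if confirmed. The documents do not support that: they contradict each other and are not uniformly restrictive. Nor does treatment or resolution in itself exclude an event. Only one that normalised before a confirming repeat, or had no repeat, is in doubt.
- **The data are still reported.** The SAP summarises abnormal laboratory values and shifts (7.10.1), vital-sign thresholds at all post-baseline visits (7.10.2), ECG interpretation and QTcF outliers (7.10.4) and BMD (7.10.5). None of these depends on a repeat or an AE record. This stands, and it confines the problem to AE-based counts. As described, though, those tables do not carry relatedness, seriousness or action taken, so they do not replace an AE record.
- **No bias between arms is shown.** Subjects, investigators and site staff stay blinded in both parts (Protocol 6.4.3). This stands. The risk is inconsistent and possibly low counts, not a shift towards one arm.
- **Confirmation screens out spurious values.** This is a fair reason to keep it for isolated findings that led to nothing. It is a weak reason where the finding was acted on.

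**Conclusion.** The conflict between 10.3.1 and 8.2.5, and within 10.3.1, is real and should be resolved. An abnormality that was acted on but not confirmed may be recorded differently across sites, and may be missing from the TEAE and SAE counts that form the Extension's primary endpoint. This assumes that at least some sites apply the first bullet of 10.3.1 as written. That is plausible because 8.3 and 10.3.4 both treat Appendix 3 as the controlling definition. The size of the loss is unknown.

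Two further inferences go beyond the documents. The first is that DXA findings at Week 48 are all lost. They have no scheduled confirmation, but a new bone diagnosis can still enter as a newly found condition, and the BMD values are summarised in any case. The second is that the primary estimand is disturbed, because a stop for an abnormality not called an AE would move from ICE-2 to ICE-3. Under SAP 7.8 all three ICE types are handled by treatment policy in the primary analysis. There, ICE type is at most a covariate for imputing missing outcomes, and it may be removed. Imputation from placebo for ICE-2 and from the subject's own arm for ICE-3 occurs only in the sensitivity analysis.

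**What to change.** Reconcile Section 10.3.1 with Section 8.2.5. State in 10.3.1 that a laboratory, ECG, imaging or vital-sign abnormality that caused symptoms, led to treatment, or led to interruption or discontinuation of IP is recorded as an AE whether or not a repeat test confirmed it. Confirmation may remain a condition for asymptomatic abnormalities on which no action was taken. This is a recording rule and changes no clinical decision.

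The cost is one sentence in a protocol amendment and a note to sites. Slightly more AEs will be recorded, a few of them from spurious values. Removing confirmation altogether, or counting every unrepeated value, would admit more spurious results and is not needed to resolve the conflict.

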10.3.2. Definition of Suspected and Unsuspected Adverse Reaction

Suspected adverse reactions are defined as:

- Any AE for which there is a reasonable possibility that the IP caused the AE. For the purposes of Sponsor regulatory safety reporting, “reasonable possibility” means there is evidence to suggest a causal relationship between the IP and the AE. A suspected adverse reaction implies a lesser degree of certainty about causality than adverse reaction, which means any AE caused by an IP.

Unexpected AEs are defined as:

- AE which is not listed in the IB of the IP or is not listed at the specificity or severity that has been observed.

10.3.3. Definition of Events to Monitor

Sponsor-defined Events to Monitor for Pegozafermin:

Events to Monitor include immunogenicity and hypersensitivity reactions occurring after the first administration of study agent(s) in subjects participating in this clinical study. These events must be reported by the Investigator to the Sponsor within 24 hours and are to be considered serious (for regulatory reporting purposes) only if they meet the definition of an SAE. These events are to be reported on an SAE form.

10.3.4. Definition of SAE

If an event is not an AE per definition in Section 10.3.1, then it cannot be an SAE even if serious conditions are met (e.g., hospitalization for signs/symptoms of the disease under study, death due to progression of disease).

An SAE is defined as any untoward medical occurrence that, at any dose:

1. Results in death

2. Is life-threatening

The term 'life-threatening' in the definition of 'serious' refers to an event in which the subject was at risk of death at the time of the event. It does not refer to an event that hypothetically might have caused death if it were more severe.

3. Requires inpatient hospitalization or prolongation of existing hospitalization

In general, hospitalization signifies that the subject has been detained (usually involving at least an overnight stay) at the hospital for observation and/or treatment that would not have been appropriate in the physician's office or outpatient setting. Complications that occur during hospitalization are AEs. If a complication prolongs hospitalization or fulfills any other serious criteria, the event is serious. When in doubt as to whether "hospitalization" occurred or was necessary, the AE should be considered serious.

Hospitalization for elective treatment of a pre-existing condition that did not worsen from baseline is not considered an SAE. Treatment or observation on an emergency outpatient basis not resulting in hospital admission is not considered an SAE.

4. Results in persistent disability/incapacity

- The term disability means a substantial disruption of a person's ability to conduct normal life functions.
- This definition is not intended to include experiences of relatively minor medical significance such as uncomplicated headache, nausea, vomiting, diarrhea, influenza, and accidental trauma

An SAE is defined as any untoward medical occurrence that, at any dose:
 
(e.g., sprained ankle) which may interfere with or prevent everyday life functions but do not constitute a substantial disruption.

5. Is a congenital anomaly/birth defect


6. Other situations:
 
Medical or scientific judgment should be exercised in deciding whether SAE reporting is appropriate in other situations such as important medical events that may not be immediately life-threatening or result in death or hospitalization but may jeopardize the subject or may require medical or surgical intervention to prevent one of the other outcomes listed in the above definition. These events should usually be considered serious.Examples of such events include invasive or malignant cancers, intensive treatment in an emergency room or at home for allergic bronchospasm, blood dyscrasias or convulsions that do not result in hospitalization, or development of drug dependency or drug abuse.

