- Evidence of hepatic decompensation including ascites, hepatic encephalopathy, splenomegaly, or variceal bleeding as assessed by the Investigator (for F4 subjects only).
- MELD Na⁺ score >12 (for F4 subjects only)

For liver chemistry abnormality actions and follow-up assessments, refer to Section [7.1.1](#).

Pregnancy is a mandatory criterion for permanent discontinuation of IP (Section [7.1.2](#)).

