7.12.1. Primary endpoint - Adverse Events

All AE summaries in primary analysis for the Main Study (described in Section 7.10.1) will be repeated for in final analysis based on safety analysis set, extend to the pooled data of both Main Study and Extension Study.

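### Whether a liver death, decompensation or liver hospitalisation counts towards the Extension's primary TEAE/SAE endpoint depends on an undefined judgement that it was expected NASH progression

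*Protocol*

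**What the plan says.** Protocol 10.3.1 lists among the events that are not AEs the disease itself or its "expected progression, signs, or symptoms of the disease/disorder being studied, unless more severe than expected" for the subject's condition. The same section lists among the events that are AEs "Exacerbation of a chronic or intermittent pre-existing condition including either an increase in frequency and/or intensity of the condition". Protocol 10.3.4 opens with a condition: an event that is not an AE under 10.3.1 cannot be an SAE "even if serious conditions are met (e.g., hospitalization for signs/symptoms of the disease under study, death due to progression of disease". Protocol 8.2.5 applies a similar filter to laboratory results: "Clinically significant abnormal laboratory findings are those that are not associated with the underlying disease", again with an exception for findings judged more severe than expected.

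The Extension's primary endpoint is "Frequency and severity of TEAEs and SAEs at Week 48" (SAP 4.2.1). SAP 7.12.1 analyses it by repeating "All AE summaries in primary analysis for the Main Study" on pooled Main and Extension data in the Safety Analysis Set, which is every randomised subject who received at least one dose (SAP 6). That set includes subjects re-read as F4, who may continue if compensated (Protocol 7.1.2). Protocol 7.1 gives, for F4 subjects only, a separate discontinuation reason: "Evidence of hepatic decompensation including ascites, hepatic encephalopathy, splenomegaly, or variceal bleeding as assessed by the Investigator".

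**The concern.** The liver is the target organ, liver injury is monitored as a possible drug effect (Protocol 7.1.1), and some cirrhotic subjects remain on study. When a subject is hospitalised or dies with worsening liver disease, the investigator must first decide whether this was expected progression. If so, the event is not an AE, and the formal causality assessment in Protocol 10.3.5, which is required for AEs and SAEs, does not apply. The question of cause is then settled before the step meant to examine it.

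At stake are the completeness of a primary safety endpoint for a small number of medically important events, and consistency between sites. Investigators are blinded, so misclassification need not differ by arm. Dropping events from both arms would still shrink any true absolute difference in such events.

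**Working it through.** The plan states no figure on this point, and the Extension safety endpoint has no stated power. The check is mainly textual, with a short calculation for scale.

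**1. The chain of definitions.** 10.3.1 removes expected progression from AEs, and 10.3.4 removes non-AEs from SAEs. Because 10.3.4 is conditional on 10.3.1, its two examples (disease-related hospitalisation and death from progression) apply only to events that 10.3.1 has already excluded. They inherit its exception for events more severe than expected.

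**2. The conflict inside 10.3.1.** Every subject has NASH, a chronic condition present at entry. A worsening of it is an AE under the inclusion list and not an AE under the exclusion list if it is judged expected. No text ranks the two lines or says what is expected at each fibrosis stage. Two sites could classify the same event differently and both follow the protocol.

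**3. Where an excluded event would be missing.**
- The Extension primary endpoint (SAP 4.2.1, 7.12.1).
- The listing of fatal events, which covers fatal AEs only (SAP 7.10.1).
- SAE reporting within 24 hours (Protocol 8.3.1).
- Causality assessment (Protocol 10.3.5).
- The count of subjects discontinuing because of TEAEs (SAP 4.2.3).

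Events to Monitor (Protocol 10.3.3) covers only immunogenicity and hypersensitivity, so it does not recover liver events. Neither document describes a hepatic-event endpoint, adjudication or an all-cause death analysis.

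**4. Where it could still be seen.**
- Discontinuation reasons, which include death and F4 decompensation (Protocol 7.1, 9.4.2; SAP 7.2).
- The suspected liver injury table and laboratory shift tables (SAP 7.10.1), which rest on laboratory values and not on AE attribution.

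Neither set of outputs would show a liver hospitalisation as such in a subject who stays on treatment.

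**5. Scale, for F4 subjects.** Input: 45% of patients with cirrhosis decompensate within 10 years of diagnosis (Protocol 2.2). Assumption: constant hazard.
- h = −ln(1 − 0.45)/10 = 0.0598 per year.
- Risk over t weeks = 1 − exp(−h × t/52), which is 2.7% at 24 weeks and 5.4% at 48 weeks.
- The number of F4 subjects is not given. The values of n below are assumptions. Expected events = n × 0.0537, and the chance of at least one = 1 − (1 − 0.0537)^n.

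| Assumed F4 subjects | Expected decompensations, 48 weeks | Chance of at least one |
|---|---|---|
| 5 | 0.27 | 24% |
| 10 | 0.54 | 42% |
| 20 | 1.07 | 67% |

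**The case against.** The strongest reply is that the exception does most of the work. The trial targets F2/F3 disease and excludes cirrhosis and decompensation at entry (Protocol 5.2, criterion 3). A liver death or decompensation in such a subject would ordinarily be more severe than expected, and so an AE and an SAE. F4 subjects continue only if compensated, without hepatocellular carcinoma and with a MELD Na⁺ score of 12 or less (Protocol 7.1.2). At about 5% over 48 weeks, decompensation is hard to call expected for them either. This stands, and it limits the point to possible loss. It does not remove the point, because the protocol leaves the judgement undefined.

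Four stronger readings are tempting, and the documents do not support them:
- A reader might take the 10.3.4 examples as unconditional. They depend on 10.3.1 and its exception.
- A reader might infer that decompensation in an F4 subject counts as expected progression, because 7.1 lists it apart from adverse events. No text says so, and death and pregnancy are also listed separately there.
- A reader might infer that the data monitoring committee would not see these events. It reviews overall unblinded safety data, and the report content is left to a charter that is not available (Protocol 9.8).
- A reader might put a figure on the share of a drug-placebo difference that would be lost. The documents give neither event rates by arm nor attribution rates.

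It is also fair to say that deleting the whole exclusion would bring routine NASH signs and disease-related laboratory values into AE reporting. That is a real trade-off, and it is not proposed here.

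**Conclusion.** The point holds in a limited form. The definitions allow serious liver events to fall outside a primary safety endpoint on an undefined judgement made before causality is assessed, and 10.3.1 pulls in two directions on the same event. How often this would happen cannot be derived from the documents.

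The numbers are small: about 0.3 to 1.1 expected decompensations over 48 weeks if 5 to 20 subjects are F4. This rests on a constant hazard, on the protocol's background rate applying to subjects selected as compensated, and on an assumed F4 count. It does not cover liver hospitalisations, or deaths from other liver causes, for which the documents give no rate. Each event would weigh heavily in benefit-risk, so a correction is worthwhile. It is an inexpensive improvement to the safety endpoint and does not call the efficacy analysis into question.

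**What to change.** 1. In Protocol 10.3.1 and 10.3.4, keep the exclusion for routine NASH signs, symptoms and laboratory values. State that every death, hepatic decompensation event and liver-related hospitalisation is recorded as an AE, and as an SAE when a seriousness criterion is met, whatever the presumed cause.
2. Delete the two examples in 10.3.4.
3. Reconcile the inclusion line on exacerbation of chronic conditions with the exclusion line in 10.3.1, and align the laboratory wording in 8.2.5.
4. In the SAP, add a table by arm of these three event types and of all-cause deaths, with a listing of all deaths in place of fatal AEs only.

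The cost is protocol wording, a notice to sites, one added table and a few more AE and SAE reports. No treatment or discontinuation rule changes.
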